#### **Unknown/unforeseeable risks**

In addition to the risks and discomforts listed here, there may be other risks that are currently not known. Subjects will be informed if any other potential risk becomes known through the duration of the study. Also, the risks and discomforts may occur more often or be more severe than have been seen before and written in this form.

#### **Benefits:**

Although our proposed study is somewhat exploratory in nature, the ideas are based on strong science and are fundamentally sound. There are many areas in which positive results may emerge; if this is determined to be the case, patient care and outcomes could benefit greatly.

#### **Costs to the Subject**

All procedures described here, including both visits and drugs, will be free of charge to patients. There is no additional cost for the subject if they participate in the study. Study related activities/procedures will be paid by the study.

#### **Data Analysis & Statistical Considerations**

Baseline data will be analyzed with Pearson product-moment correlations, multiple regression, and (if clinically relevant group demarcation can be established, ANOVA). Intervention data will be analyzed primarily by repeated-measures ANOVA.

With our location in the Duke Eye Center, we foresee no issues in terms of patient recruitment or convenience for patient visits. Additionally, we have access to all of the experimental equipment (listed above) and other resources required to conduct the study.

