### **Study Design & Procedures**

The proposed study design is a randomized, double-masked, placebo-controlled one-year intervention in glaucoma patients with moderate to advanced disease. The total period of performance for this study (to allow for recruitment, experimental visits, analysis, and final report) would be 24 months.

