#### **General evaluation:**

The following is a list of assessments to be conducted at each patient visit.

1. Measurement of MPOD. Equipment: The Heidelberg Spectralis with MPOD module will be used to obtain an MPOD spatial density profile; no dilation required. Patient time: 15 minutes.

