### **Selection of Subjects**

All participants must have signed the consent form. A power analysis based on previous retinal response and corresponding visual performance data from AMD patients revealed that 30 patients each in both placebo and treatment groups would be required to detect effects, if present. Assuming some attrition, we plan to recruit a total of 60 patients, half of which would be randomly assigned to receive a macular carotenoid supplement, containing 10 mg L, 2 mg Z, and 10 mg MZ (to be consumed once daily with a meal). In terms of macular carotenoid content, 22 mg total is roughly equivalent to 2 large bowls of spinach. The other half would receive an identical pill, containing only sunflower oil (as with the active supplement, patients would be instructed to take one pill daily, with a meal). Baseline measures (see below) for patients consenting to enroll in the study would be determined shortly after enrollment, prior to the onset of supplementation.

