### **Scheduled Visits**

Patients will be assessed at baseline, 3 months and 6 months (final visit).

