**PI: [name], Ph.D**

All statistical analyses will be performed by [name] and associates using commercially available statistical and mathematics software Stata (version 15; StataCorp LP, College Station, TX, USA), MATLAB (Mathworks, Inc.), and MPLUS (Muthen & Muthen). An alpha level will be generally set at 0.05, unless there is a need to correct for multiple comparison testing which will then be performed by procedures such as false discovery rate.

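### The primary intervention analysis states no adjustment for the baseline value; for a given arm contrast, adding it is a modest gain in precision at very little cost

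*Combined protocol and SAP*

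**What the plan says.** Under Data Analysis & Statistical Considerations, one sentence covers the randomised comparison: "Intervention data will be analyzed primarily by repeated-measures ANOVA". It gives no covariate, does not say whether baseline is a level of the visit factor, and names no effect or contrast to be tested. Multiple regression is mentioned only for the cross-sectional baseline data. The same section adds only the software and the error rate: "An alpha level will be generally set at 0.05, unless there is a need to correct for multiple comparison testing".

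The data for an adjusted analysis will exist. Under Selection of Subjects, baseline measures "would be determined shortly after enrollment, prior to the onset of supplementation". Under General evaluation, "The following is a list of assessments to be conducted at each patient visit", and Scheduled Visits lists baseline, 3 months and 6 months. On size, Selection of Subjects says that "30 patients each in both placebo and treatment groups would be required to detect effects, if present", and plans to recruit 60 in total.

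**The concern.** The planned sentence has two usual readings. If baseline is a level of the visit factor, a 1-df arm contrast at a later visit compares change from baseline. If only the follow-up visits enter, the contrast compares unadjusted follow-up values. Neither conditions on baseline.

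A change score fixes the baseline slope at 1, and the unadjusted comparison fixes it at 0. Adjustment estimates the slope and so usually leaves less residual variance. Recruitment equals the number said to be required, with some attrition expected, so the sample has no slack. Precision that can be had from data already collected is worth taking.

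**Working it through.** **Inputs from the documents.** 30 per arm, 1:1; alpha 0.05 (taken as two-sided); baseline plus two follow-up visits.

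**Assumed, because the documents do not give them.** Baseline-to-follow-up correlation r; ratio k of follow-up SD to baseline SD; effect size; no dropout.

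**The plan's own figure.** The 30 per arm cannot be reproduced, since no effect size, SD or power is stated. Inverting the normal approximation at 80% power, (1.960 + 0.842) × √(2/30) = 0.723 SD.

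**Variance factors for one follow-up visit, 1-df arm contrast** (baseline SD = 1):
- unadjusted follow-up value: k²
- change from baseline: k² + 1 − 2rk
- baseline-adjusted: k²(1 − r²) × 57/56, where (N − 3)/(N − 4) = 57/56 at N = 60 is the price of estimating the slope

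With k = 1 and r = 0.7, change is 2(1 − 0.7) = 0.60 and adjusted is 0.51 × 1.018 = 0.519, a ratio of 0.87. Over the range:

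| r | adjusted / change, k = 1 | adjusted / change, k = 1.25 | adjusted / unadjusted |
|---|---|---|---|
| 0.5 | 0.76 | 0.91 | 0.76 |
| 0.7 | 0.87 | 1.00 | 0.52 |
| 0.8 | 0.92 | 1.02 | 0.37 |
| 0.9 | 0.97 | 0.97 | 0.19 |

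**Where adjustment loses.** Against change, the loss arises where the baseline slope rk is near 1.
- k = 1: solving (1 + r)/2 × 57/56 = 1 gives r = 0.965, so adjustment loses only above about 0.96.
- k = 1.1: r from about 0.84 to 0.95.
- k = 1.25: r from about 0.71 to 0.87.

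Against the unadjusted value, (1 − r²) × 57/56 = 1 gives r = 0.132, so adjustment loses only below about 0.13. The loss never exceeds 57/56 − 1 = 1.8% of variance. If the SD falls after baseline (k below 1), the gain over change is larger than in the k = 1 column.

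**In patients.** With k = 1, a change-score contrast matches 30 adjusted patients per arm with 30/0.763 = 39.3, 30/0.865 = 34.7 and 30/0.916 = 32.7 per arm at r = 0.5, 0.7 and 0.8.

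**In power** (noncentral t, k = 1, effect 0.5 SD, final visit; 58 df for change, 57 for adjusted):

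| r | change | adjusted |
|---|---|---|
| 0.5 | 47.8% | 58.7% |
| 0.7 | 69.1% | 75.2% |
| 0.8 | 85.3% | 88.2% |
| 0.9 | 98.9% | 99.1% |

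The unadjusted comparison has 47.8% at every r. If the effect is instead set so that change has 80% power, adjustment has about 89, 85, 83 and 81% at these four correlations (normal approximation).

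**Mean of the two follow-up visits** (equal SDs, equal correlations, constant 0.5 SD effect): change against adjusted is 59.4 v 76.1%, 81.0 v 88.2% and 93.5 v 95.9% at r = 0.5, 0.7 and 0.8.

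**A different test.** A 2-df group-by-visit test is not the same contrast. By simulation with first-order autoregressive correlation 0.8, sphericity-corrected:
- constant 0.5 SD effect: 2-df test about 74%, adjusted final-visit contrast about 69%, adjusted follow-up mean about 87%
- effect building from 0.25 to 0.5 SD: about 59%, 69% and 63%

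The order depends on the effect pattern, which the documents do not give.

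**The case against.** The strongest reply has four parts.

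- **The planned test may not be a 1-df contrast.** Repeated-measures ANOVA is naturally read as an omnibus group-by-visit test, and moving from that to one adjusted final-visit contrast can lose power. This stands. A reader might infer that adjustment improves on whatever the plan would have tested; the documents do not support that, because they name no contrast. The gain belongs to adjusting a given contrast, not to choosing one.
- **The gain depends on equal SDs.** This also stands. With k = 1.25 the advantage over change vanishes at r = 0.7 and is a loss of about 2% at 0.8. But no case loses more than that.
- **The plan may already use baseline, or intend to adjust.** If baseline is a visit level, it is used as a change score, so it would be wrong to say that the plan ignores it. Because the sentence says that ANOVA is used primarily, adjusted analyses are not excluded. Neither point puts adjustment into the primary analysis.
- **The study is small and exploratory.** The Benefits section says "Although our proposed study is somewhat exploratory in nature". That lowers the priority, but it is no reason to leave precision unused.

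A reader might also infer that unadjusted repeated-measures ANOVA is biased or invalid. It is not: under randomisation the arm comparison remains valid without adjustment.

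**Conclusion.** The point holds as a matter of efficiency. The primary intervention analysis states no baseline adjustment. For the same 1-df arm contrast, adding it ranges from a loss of about 2% of variance to a useful gain. Over r = 0.5 to 0.9, the reduction in variance relative to change is about 24% to 3% with equal SDs, and between 9% and nothing (with a loss of about 2% at r = 0.8) with an SD ratio of 1.25. Relative to an unadjusted follow-up comparison it is larger, about 48% at r = 0.7.

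All of this rests on assumed correlations and SD ratios, 30 analysed per arm and no dropout. It does not show that 30 per arm is too few, since the basis of that number is not given. The change is worth making before unmasking, but the trial's validity does not depend on it.

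**What to change.** In Data Analysis & Statistical Considerations, state that the primary arm comparison for each intervention outcome will include that outcome's baseline value as a covariate, with the follow-up visits as the repeated measures (ANCOVA, or a mixed model for the post-baseline visits). Name before unmasking the one arm contrast that is tested, either the mean over follow-up visits or the final visit, and report it with a 95% CI. Repeated-measures ANOVA may stay as a supporting analysis.

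**Cost.** A change of wording and one extra parameter. No new patients, visits or measurements are needed, and Stata, already listed, can fit the model. The choice of contrast can gain or lose power depending on how the effect develops, so it should follow the pattern the investigators expect.

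**Separate point.** Study Design & Procedures describes a "placebo-controlled one-year intervention in glaucoma patients with moderate to advanced disease", while Scheduled Visits ends at 6 months. These passages must be reconciled before a final-visit contrast is defined.

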**PI: [name], Ph.D**

### **Risk/Benefit Assessment**

#### **Risks**

Risks from participating in the study are low. The primary risks for all participants are some discomforts, which are similar to those encountered in any complete eye examination. Participants will undergo non-invasive procedures used for diagnostic purposes. All medical instruments are FDA approved. The software for OCT Angiography and Macular pigment optical density analysis are currently undergoing FDA review and are not currently approved.

Lutein, zeaxanthin, mesozeaxanthin are over-the-counter nutritional supplements from natural sources. Lutein, zeaxanthin, mesozeaxanthin are likely safe when taken by mouth appropriately. There are no known risks or drug interactions associated with macular carotenoids as part of the diet. They are likely safe when used in the amounts found in food for pregnancy and breast-feeding

There is, however, the potential risk of loss of confidentiality. Every effort will be made to keep the information confidential; however, this cannot be guaranteed. Some of the questions that will be asked as part of this study may make the patients feel uncomfortable. Patient may stop their participation in this study at any time.

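### Repeated-measures ANOVA is the main intervention analysis, but the plan does not say how patients with missed visits are handled; an all-randomised mixed model is a cheap improvement

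*Combined protocol and SAP*

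**What the plan says.** The section Data Analysis & Statistical Considerations gives the intervention analysis in one sentence: "Intervention data will be analyzed primarily by repeated-measures ANOVA". It names three software packages and a significance level ("An alpha level will be generally set at 0.05"), but no model terms, covariance structure or command.

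Other sections set the conditions in which this analysis will run:

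- Scheduled Visits: "Patients will be assessed at baseline, 3 months and 6 months (final visit").
- Study Design & Procedures describes the trial as a "randomized, double-masked, placebo-controlled one-year intervention in glaucoma patients with moderate to advanced disease", which does not agree with a final visit at 6 months.
- Selection of Subjects: "Assuming some attrition, we plan to recruit a total of 60 patients". The same section says that the power analysis "revealed that 30 patients each in both placebo and treatment groups would be required to detect effects, if present".
- Risks: "Patient may stop their participation in this study at any time".

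No section states an analysis set, an intention-to-treat rule, a missing-data method, or whether patients who stop the capsules are still followed.

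**The concern.** Repeated-measures ANOVA is not one procedure. The classical form, with one row per patient, needs a value at every visit. A patient who leaves after month 3 then contributes nothing, although baseline and month 3 were measured. A patient who misses only month 3 loses an observed month-6 result. The comparison is among completers rather than among patients as randomised. A long-format fit, with one row per visit, keeps partial records. The protocol does not choose between them, so which randomised patients count could be settled after the data are seen.

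Two things are at stake. One is precision, in a trial of only 60 patients. The other is bias, if leaving is related to outcome and especially if that relation differs by arm. Recruiting more patients would restore precision but would not remove such bias.

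**Working it through.** **The plan's own figure.** The 30 per arm cannot be reproduced, because effect size, SD, power and sidedness are not stated. Solving backwards with a two-sided 0.05 level and 80% power (both assumed): d = (1.960 + 0.842) × √(2/30) = 0.723 SD. Recruitment of 60 equals 2 × 30, so the expected attrition has no allowance. The point below does not depend on this figure.

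**Patients lost to complete-visit deletion.** The documents give no attrition rate. Assume that baseline is always observed and that a share m misses each of the two follow-up visits independently. The share with all visits is (1−m)². The share with month 6 observed is 1−m. The ratio of confidence-interval widths at month 6 is 1/√(1−m).

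| m | All visits, of 60 | Dropped | Month 6 observed, of 60 | CI ratio |
|---|---|---|---|---|
| 5% | 54.2 | 9.75% | 57 | 1.026 |
| 10% | 48.6 | 19% | 54 | 1.054 |
| 15% | 43.4 | 27.75% | 51 | 1.085 |

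At m = 10%, power starting from an assumed 80% is about 71% with 24.3 complete patients per arm. It is about 76% with the 27 per arm who have a month-6 value. So roughly half of the fall comes from the missing month-6 results themselves and half from the deletion rule. If patients only drop out and never skip a visit, deletion removes nobody extra at month 6; what it discards is their month-3 data.

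**Bias, by simulation.** Set-up: 30 per arm, three visits, SD 1, true arm difference 0.25 SD at month 3 and 0.50 SD at month 6, dropout only after month 3. Estimates are the arm difference in change from baseline to month 6.

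- *Completely random dropout.* The complete-visit estimate is unbiased. Its variance is about 3-6% higher than that of the likelihood model, so the interval is √1.03 = 1.015 to √1.06 = 1.030 times as wide.
- *The same outcome-related dropout in both arms.* The complete-visit estimate is 0.48-0.49 against 0.50. A second set-up with a true effect of 0.70 gave 0.67, with 0.70 from the likelihood model. The shift is 0.01-0.03 SD.
- *Dropout that differs by arm.* In placebo, logit(dropout) = logit(0.1 or 0.2) − 1.5 × (3-month change). In active, dropout is random at 0.1 or 0.2. Total loss is 12-23%. With every between-visit correlation at 0.6, the complete-visit estimate is 0.43 or 0.38; at 0.8 it is about 0.47 or 0.43. The shift is 0.50 − 0.47 = 0.03 to 0.50 − 0.38 = 0.12 SD. The likelihood estimate stays at about 0.50. In the second set-up (5% random loss on active), a true effect of zero came out as −0.09 with deletion and 0.00 with the likelihood model.
- *Long-format ANOVA in that asymmetric scenario.* With equal correlations it gives 0.50 throughout. With correlations of 0.7 (baseline to month 3), 0.5 (baseline to month 6) and 0.8 (month 3 to month 6) it gives 0.44 or 0.41.

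For scale, the standard error of the month-6 estimate in these simulations is 0.17-0.26 SD.

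**The case against.** The strongest reply is that the plan never says incomplete patients will be deleted. That is right. A reader might infer from the words repeated-measures ANOVA that every patient with a missed visit will be thrown out, but the text does not support it. The long-format version of the named method keeps partial records, and under equal correlations it was unbiased even in the scenario least favourable to deletion. The bias figures therefore belong to complete-case deletion and not to ANOVA as such.

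The arm-differential scenario is also an assumption. The trial is double-masked with a matching placebo, visits are free, payment is tied to completion, and only one visit remains after month 3. Nothing in the documents shows that placebo patients would leave for different reasons. The sentence allowing withdrawal is a standard right and says nothing about rates. With a shared mechanism the shift is small beside the standard error. The protocol also describes the study as partly exploratory.

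All of this stands, and it limits the size of the point. It does not remove it. The plan leaves the form of the analysis open, and the long-format version loses its protection once correlations differ between visits, which the plan gives no reason to exclude.

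**Conclusion.** The point holds as a cheap improvement. The plan names a primary method whose classical form drops every patient with a missed visit, expects attrition, and has no rule for incomplete patients. Under the assumed miss rates that form would drop about 10-28% of patients. The cost is mainly precision if dropout is random. The month-6 shift is about 0.01-0.03 SD if outcome-related dropout is alike in both arms, and about 0.03-0.12 SD in the assumed asymmetric scenario. These sizes rest on equal correlations of 0.6-0.8 and on complete-visit deletion; they are illustrations, not bounds.

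Two stronger readings should be resisted. One is that the trial's result will be biased: that needs outcome-related dropout and a particular fit, and the documents establish neither. The other is that the ANOVA would create a false benefit: in the asymmetric scenario the shift runs against the supplement, and the real direction cannot be known from the documents.

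**What to change.** In Data Analysis & Statistical Considerations, make the main intervention analysis a likelihood-based mixed model for repeated measures. Specify arm, visit and arm-by-visit terms, an unstructured covariance, and REML with a small-sample degrees-of-freedom correction such as Kenward-Roger. The Stata already named can fit it. State that all randomised patients are analysed in their assigned arm with every visit they attended. Keep the completer ANOVA as a secondary analysis.

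In Scheduled Visits, state that patients who stop the capsules without withdrawing consent are still invited to the remaining scheduled visits and analysed as randomised. Nothing in the protocol ends their visits now, so this is a clarification.

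Reconcile the one-year intervention in Study Design & Procedures with the 6-month final visit in Scheduled Visits, because these passages determine which visits enter the model.

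The analysis and follow-up changes cost a few sentences, with no added visits or patients. There are two downsides. The model assumes that dropout is explained by the observed results, and the completer ANOVA does not test that assumption. Data collected after patients stop the capsules may also slightly dilute the estimated effect.

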At baseline, our proposed study has the potential to determine cross-sectional relationships between MPOD, visual performance, and disease severity in glaucoma. Given the recent data from Siah et al. (2017), significant relationships are plausible – and if we determine these kinds of relationships, standard of care for glaucoma patients could be changed to include improved patient education regarding nutrition. Additionally, visual function testing (to include CS, DA, and DG testing) may be instituted for glaucoma suspects and established glaucoma patients. If we are able to show an acute effect of improvement in visual performance, disease parameters, or even simply increases in MPOD in glaucoma patients upon supplementation with macular carotenoids, it could lead to larger trials that may yield extremely important data with regard to management of glaucoma. Given the predicted exponential increase in worldwide glaucoma prevalence (76 million in 2020 to 111.8 million in 2040; Tham et al. [2014]), strategies that may delay the onset of visual disturbance or prolong good visual function would be hugely significant.

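### The repeated-measures ANOVA for the randomised data names no term, contrast or visit as the treatment test, and its possible tests differ in meaning and power

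*Combined protocol and SAP*

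**What the plan says.** Under Data Analysis & Statistical Considerations, the randomised data get one sentence: "Intervention data will be analyzed primarily by repeated-measures ANOVA". The same section adds software, then "An alpha level will be generally set at 0.05", with a correction such as false discovery rate if multiple testing is judged to need it. It does not list the levels of the repeated factor. It names no model term, contrast, visit or baseline adjustment as the basis for the treatment comparison, and no other section does so.

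The design facts that bear on this are elsewhere. Scheduled Visits says "Patients will be assessed at baseline, 3 months and 6 months (final visit"). Selection of Subjects says baseline measures "would be determined shortly after enrollment, prior to the onset of supplementation", and that "30 patients each in both placebo and treatment groups would be required to detect effects, if present". Study Design & Procedures calls the trial a "randomized, double-masked, placebo-controlled one-year intervention in glaucoma patients with moderate to advanced disease".

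**The concern.** Two arms and three visits give a repeated-measures ANOVA three F-tests for every outcome, and they answer different questions.

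- **Arm main effect.** This compares the arms on the average over all visits. If baseline is one of those visits, it carries no treatment effect and pulls the estimate towards zero.
- **Time main effect.** This pools the arms. It is not a randomised comparison and says nothing about the supplement.
- **Arm-by-time interaction.** This is a valid randomised test. With three visits it has 2 df, so a significant result gives no direction, no size and no visit.

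The same data on one outcome can therefore be called positive or negative depending on which line of the ANOVA table is read. If the choice is made after seeing the results, the 5% level is not protected. Naming a single primary outcome would not settle this, because that outcome would still have three tests. It also means that the 30 per arm cannot be tied to any particular test.

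**Working it through.** **Inputs from the documents.** 30 per arm, 60 in total (Selection of Subjects); visits at baseline, 3 and 6 months (Scheduled Visits); baseline before supplementation (Selection of Subjects); alpha 0.05, sidedness not stated (Data Analysis & Statistical Considerations).

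**Assumed, because the documents give no values.** Two-sided tests; SD 1 at each visit; equal correlation ρ between visits of 0.5, 0.7 or 0.8; no dropout; all three visits in the model.

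**The plan's own figure.** The 30 per arm cannot be reproduced, since no effect size, SD, power or test is given. Back-solving with the normal approximation for 80% power, two-sided: √(2/30) × (1.960 + 0.842) = 0.72 SD. With the t distribution on 58 df it is 0.7356 SD, used below.

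**Step 1: dilution of the arm main effect.** Let d be the effect at 6 months.
- Half present at 3 months: (0 + d/2 + d)/3 = d/2.
- Fully present at 3 months: (0 + d + d)/3 = 2d/3.

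**Step 2: false positives with no effect.** The arm and interaction tests behave almost as independent tests. Accepting either at 0.05 gives about 1 − 0.95² = 0.0975. Simulation gives 0.095 to 0.10 across the correlations. The arm test alone stays near 0.05.

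**Step 3: power.** Size d for 80% power on the 6-month change: d = 0.7356 × √(2(1 − ρ)) = 0.74, 0.57 and 0.47 for ρ = 0.5, 0.7 and 0.8. Then:
- Arm main effect, half present at 3 months: noncentrality = (d/2) / √[(2/30)(1 + 2ρ)/3]. At ρ = 0.5 this is 0.368/0.211 = 1.74.
- Interaction: noncentrality = 15 × S × d²/(1 − ρ), on 2 and 116 df. S is the sum of squared deviations of the effect profile from its mean, in units of d²: 1/2 if half is present at 3 months, 2/3 if all is. This gives 8.1 and 10.8 at every ρ.
- Change contrast: noncentrality = d / √[(2/30) × 2(1 − ρ)] = 2.85 at every ρ.
- Baseline-adjusted final-visit contrast: noncentrality = d / √[(2/30)(1 − ρ²)] = 3.29, 3.09 and 3.00, slightly reduced for estimating the baseline slope.

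| Test | Half present at 3 months (ρ 0.5 / 0.7 / 0.8) | Fully present at 3 months |
|---|---|---|
| Arm main effect | 0.40 / 0.23 / 0.16 | 0.63 / 0.37 / 0.25 |
| Arm-by-time, 2 df | 0.71 / 0.71 / 0.71 | 0.84 / 0.84 / 0.84 |
| 6-month change, 1 df | 0.80 / 0.80 / 0.80 | 0.80 / 0.80 / 0.80 |
| Baseline-adjusted, 6 months, 1 df | 0.89 / 0.85 / 0.83 | 0.89 / 0.85 / 0.83 |

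Simulation agrees with these figures to within about 0.01.

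**Step 4: disagreement.** With half the effect present at 3 months, the arm and interaction tests gave opposite verdicts in 54%, 62% and 64% of simulated trials.

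**The case against.** The strongest reply is that the defect is underspecification rather than a wrong analysis. The analysis section treats baseline data and intervention data in separate sentences and never lists the repeated levels, so an ANOVA on change scores or on post-baseline visits is not excluded. On those readings the arm main effect is not diluted. On mean change, with the full effect present by 3 months, its power is 0.90 at every correlation. This stands: the dilution figures belong to one reading only. It does not rescue the plan, because which reading applies is what the plan leaves unsaid.

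Second, many analysts would take the interaction as the treatment test by convention, and the multiplicity clause could be applied to the rest. But the plan does not name the interaction, and the interaction alone leaves direction, size and visit open. The clause is conditional and defines no family of tests.

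Third, the Benefits section describes the study as partly exploratory. That lowers the stakes, but the trial is randomised and placebo-controlled and claims a power analysis.

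A reader might also infer that the investigators mean to count a change over time as efficacy, because Background & Significance speaks of "an acute effect of improvement in visual performance, disease parameters, or even simply increases in MPOD in glaucoma patients". The documents do not support that. The sentence goes on to tie the improvement to taking the supplement, it looks ahead to larger trials rather than setting a success criterion, and nothing proposes ignoring the placebo arm.

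**Conclusion.** The concern holds as a gap in the plan: no treatment contrast is named for the randomised data. If all three visits enter the model, the candidate tests differ materially. Accepting either arm-related term uncorrected roughly doubles the per-outcome error rate, to about 9.5 to 10%. For an effect half present at 3 months, power runs from 0.16 to 0.41 (arm effect, allowing for simulation error) through about 0.71 (interaction) to 0.83 to 0.89 (baseline-adjusted final-visit contrast). These figures rest on the assumed correlations, effect shapes and complete follow-up. No dropout rate is given, and the 60 recruited equal the 30 per arm said to be required.

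Two stronger conclusions might be drawn and should not be. One is that the arm main effect is invalid or misses most real effects: it keeps its 5% type I error, and its power reaches 0.63 at a correlation of 0.5 when the effect is complete by 3 months. The other is that the trial will run at a 10% error rate: that follows only if either term is accepted without the correction that the plan allows for. This should be changed before the data are analysed; it does not undermine the design.

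**What to change.** In Data Analysis & Statistical Considerations, replace the ANOVA sentence with wording such as:

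> For each intervention outcome, the treatment effect is the single two-sided, 1-df difference between arms at the final visit, adjusted for the baseline value of that outcome, estimated from the repeated-measures model (or ANCOVA) and reported with its 95% confidence interval. The arm main effect over all visits and the time main effect are not used as evidence of a supplement effect. The omnibus arm-by-time test and the 3-month contrast are supportive.

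Before the visit is fixed, the one-year intervention in Study Design & Procedures and the 6-month final visit in Scheduled Visits must be reconciled.

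The cost is a few lines of text, with no new patients, visits or data. The downside is that the test looks only at the final visit. If the effect is already complete by 3 months and the correlation is high, little or nothing is gained over the 2-df interaction (0.83 against 0.84 at a correlation of 0.8), though direction, size and visit are still gained.
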